## 4.4 Eligibility

### 4.4.1 Inclusion criteria

Shahi employees will be eligible to participate if:

- they are aged 30 years or older
- have presbyopia, defined as an unaided near visual acuity of N6.3 or worse in both eyes
- have worked in the production department for 6 weeks or more
- they require a new pair of glasses to improve their near vision
- they have a corrected near visual acuity of N4 or better in both eyes

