### 4.4.2 Exclusion criteria

Shahi employees will be ineligible to participate if:

- have ocular pathology in either eye detected during the eye examination, or history of such disease based on self-report
- have a low likelihood of completing follow-up in the study due to current plans to move out of the area or leave employment at Shahi during the follow-up period

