## 5. PROTOCOL DEVIATIONS

A protocol deviation is defined as a failure to adhere to the protocol such as the wrong intervention being administered, incorrect data being collected and documented, errors in applying inclusion/exclusion criteria or missed follow-up visits due to error.

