### 5.2.1 Participants randomised in error

- Employees < 35 years, or employed < 6 weeks, or not employed in the sewing department assigned to Intervention Group

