### 7.2 Descriptive analysis population

Baseline demographic and clinical characteristics will be reported for all workers randomised for whom we have data available, excluding protocol deviations randomised in error where Informed Consent has not been obtained.

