### 8.1 Representativeness of trial population and participant throughput

The flow of participants through each stage of the trial will be summarised using a CONSORT diagram (see below). We will report the numbers of participants:

- at participating sites
- eligible for eye examination
- examined
- stratified and randomly assigned
- received intended intervention
- withdrawals
- randomised in error

included in the analysis

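### SAP 5.2.1 ties its definition of randomisation in error to the Intervention Group and omits the vision criteria, so the count reported under 8.1 is asymmetric by arm and incomplete

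*SAP*

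**What the plan says.** Section 5 gives a general definition of a protocol deviation. It includes "errors in applying inclusion/exclusion criteria or missed follow-up visits due to error" and is not limited to one arm or to particular criteria. Sections 5.1 and 5.2 then list the major and minor deviations.

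The minor category for participants randomised in error (5.2.1) consists of one bullet. It names employees under 35, "or employed < 6 weeks, or not employed in the sewing department assigned to Intervention Group". There is no bullet for Control.

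The eligibility criteria are in 4.4. Among the inclusion criteria are "have presbyopia, defined as an unaided near visual acuity of N6.3 or worse in both eyes" and "they have a corrected near visual acuity of N4 or better in both eyes". Among the exclusions, workers are ineligible if they "have ocular pathology in either eye detected during the eye examination". The lower age limit in 4.4.1 is 30, and the department named there is production.

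The label is used in two other places. Section 8.1 lists "randomised in error" among the numbers to be reported with the CONSORT diagram. Section 7.2 describes baseline characteristics of all randomised workers with data, "excluding protocol deviations randomised in error where Informed Consent has not been obtained".

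**The concern.** Whether a worker met the entry criteria is settled before allocation. Section 4.9 keeps the sequence concealed until a worker is found eligible and agrees to take part. A breach of eligibility therefore cannot depend on the arm drawn, and a definition of it should not mention an arm. Arm-specific wording belongs in 5.2.2, where failing to receive the allocated intervention does mean different things in the two groups.

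The CONSORT flow is at stake. If 5.2.1 is followed as written, a difference between arms in the reported number of ineligible workers may come from the definition alone, and a reader could take it for a difference in how the arms were enrolled. The definition also leaves out the vision criteria, so the reported count cannot show how well the trial kept to its target population of workers with correctable presbyopia.

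**Working it through.** **The plan's own group size.** The only planning figure used below is 630 per group (4.8). It can be reproduced. The Schoenfeld formula for a hazard ratio of 0.8, two-sided 5% and 80% power gives 4 × (1.960 + 0.842)² / (ln 0.8)² ≈ 631 events. Dividing by the 50% one-year leaving rate in Control gives 631 / 0.5 = 1,262, against 1,260 stated. The point made here does not affect this figure.

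**Criteria in 4.4 against the list in 5.2.1.**

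| Criterion in 4.4 | In 5.2.1? |
|---|---|
| Aged 30 or over | Age is listed, but with a limit of 35 |
| At least 6 weeks in production | Employment under 6 weeks is listed; the department is sewing |
| Unaided near acuity N6.3 or worse, both eyes | No |
| Needs new glasses for near | No |
| Corrected near acuity N4 or better, both eyes | No |
| Ocular pathology, found or self-reported (exclusion) | No |
| Unlikely to complete follow-up (exclusion) | No |

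Five of the seven criteria are absent, including all three vision criteria and the ocular exclusion. The two that are covered do not match 4.4.1. As the text stands, an Intervention worker aged 30 to 34 meets the age criterion in 4.4.1 and is still labelled an error under 5.2.1.

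**Against section 5.** A Control worker with 4 weeks' employment, or a worker in either arm with ocular pathology, is a deviation under the general definition but appears in neither the major nor the minor list.

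**The two readings of the arm qualifier.**

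- Plain reading: it governs the whole bullet. No Control breach of age, tenure or department is counted.
- Narrow reading: it governs only the department item. Age and tenure breaches count in both arms, but no Control department breach is counted.

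Both readings are asymmetric.

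**Size on the plain reading.** The documents give no breach rate, so a rate *r* for the listed criteria, equal in both arms, is assumed. Expected breaches per arm are 630 × *r*:

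- *r* = 1%: 630 × 0.01 = 6.3, about 6
- *r* = 2%: 630 × 0.02 = 12.6, about 13
- *r* = 5%: 630 × 0.05 = 31.5, about 32

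The Control figure reported would be 0 in each case. On the narrow reading only the department share of these is lost, and the documents do not allow that share to be estimated. Vision breaches come on top, uncounted in both arms on either reading.

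**Reach into the analyses.** Section 7.1 analyses all participants as allocated, for all outcomes. Section 7.2 removes only workers without consent, and only from the baseline description. Section 9.6 does not mention the label. The hazard ratio is therefore not touched.

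**The case against.** The strongest reply is that this is loose drafting with little consequence. Several parts of that reply stand.

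- **Bias in the primary comparison.** A reader might infer that a one-sided label leads to one-sided exclusions and damages the randomised comparison. The SAP does not support this. Analysis is by intention to treat; 7.2 removes nobody for age, tenure, department or vision; and 9.6 provides a blinded review, discourages exclusions and requires documented reasons before database lock.
- **Dilution.** A reader might also infer that workers who breach the vision criteria cannot benefit from glasses and so weaken the effect. No section says so. Eligibility is determined before allocation is revealed, so such breaches may also be few.
- **A certain zero in Control.** For age and tenure this depends on how the final phrase attaches. Moreover, 7.2 applies the label to missing consent, which 5.2.1 does not list, so the SAP itself uses the term loosely. Section 8.1 does not cite 5.2.1 or restrict the count by arm.
- **The breach rates.** They are assumptions. Because the age and department wording differs from 4.4.1, the label would also not count exactly the true breaches.

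Three things survive. Section 5.2.1 is the only definition offered, it is narrower than section 5 and inconsistent with 4.4, and it is asymmetric on either reading. This is not a detail left to the protocol: the SAP sets the rule itself, and following it gives a wrong count.

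**Conclusion.** The definition is wrong as written, with an impact confined to reporting. The count under 8.1 would omit all Control breaches on the plain reading, or all Control department breaches on the narrow one, and would omit vision and ocular breaches in both arms. On the plain reading about 6 to 32 Control breaches would go uncounted, assuming equal breach rates of 1% to 5% and 630 per group. The intention-to-treat hazard ratio and the sample size are unaffected, and no participant is excluded on this label apart from the no-consent removal in 7.2. The age and department conflict between 5.2.1 and 4.4.1 must be reconciled before the count has a clear meaning; the documents do not settle which wording is intended.

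**What to change.** 1. Reconcile the age limit and department in 5.2.1 with 4.4.1.
2. Then replace the bullet in 5.2.1 with: *any participant in either group who, on information recorded before randomisation, failed any criterion in 4.4.1 or met any in 4.4.2.*
3. In 8.1, report the number by arm and by criterion.
4. State that all such participants stay in the intention-to-treat analysis.
5. In 7.2, state the no-consent removal as a rule of its own that applies to both arms. Missing consent is a major deviation under 5.1 and is not part of 5.2.1.

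The cost is SAP wording only. Section 4.10.1 already provides for human-resources data and an eye examination form before the trial, which should cover most of the criteria. The one small downside is that the reported number of deviations may rise.

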### 5.2.2 Participants who do not receive allocated intervention

- Workers in the Intervention Group not receiving glasses
- Workers in the Control Group received glasses from VisionSpring (workers in the Control Group deciding to purchase glasses from an external eyecare service provider during the course of the study will not be considered a protocol deviation, and their data will be analysed under the Intention-to-treat principle)

## 6. ADHERENCE TO THE INTERVENTION

Adherence to the intervention will be assessed through observation of spectacle wear while working. Adherence will be measured surreptitiously on a weekly basis. The enumerators assessing spectacle wear compliance are GBL staff members familiar to Shahi workers but are not revealed to be collecting glasseswear adherence data to ensure minimum modification of compliance behaviour in present of enumerators.

## 7. ANALYSIS POPULATIONS

### 7.1 Primary analysis strategy

All outcomes will be assessed by Intention-to-treat (ITT): participants will be analysed in the groups into which they were randomly allocated, i.e. comparing the outcomes of all workers allocated to the Intervention Group with workers allocated to the Control Group, regardless of allocation received.

### 7.2 Descriptive analysis population

Baseline demographic and clinical characteristics will be reported for all workers randomised for whom we have data available, excluding protocol deviations randomised in error where Informed Consent has not been obtained.

## 8. DESCRIPTIVE ANALYSES

[figure not shown]
### 8.1 Representativeness of trial population and participant throughput

The flow of participants through each stage of the trial will be summarised using a CONSORT diagram (see below). We will report the numbers of participants:

- at participating sites
- eligible for eye examination
- examined
- stratified and randomly assigned
- received intended intervention
- withdrawals
- randomised in error

included in the analysis

## CONSORT Flow Diagram

## 8.2 Baseline comparability of randomised groups

Participants in randomised groups will be described separately with respect to the following characteristics at trial entry:

- age
- sex
- education level
- marital status
- number of children and dependants
- median wage compared to urban Bangalore and urban India
- near vision quality of life (THRIVE tool)
- uncorrected visual acuity in each eye separately at distance and both eyes together at near
- urban or rural factory

- mean power of near correction required
- baseline work productivity
- worker self-efficacy
- attitudes towards vision correction
- access to local eyecare services
- history of uptake of eyecare services

Numbers (with percentages) for binary and categorical variables and means (and standard deviations), or medians (with lower and upper quartiles) for continuous variables will be presented; there will be no tests of statistical significance performed nor confidence intervals calculated for differences between randomised groups on any baseline variable.

### **8.3 Losses to follow-up**

Whilst high degrees of loss-to-follow-up can lead to biased estimates of the intervention effect (particularly when there is differential drop out between intervention arms, which is related to the intervention) we anticipate minimal loss-to-follow-up with respect to the primary outcome and for secondary outcomes. In the case of the primary outcome, loss of employment at Shahi, “loss to follow-up” is in and of itself an endpoint. We will perform complete-cases analyses in each case. With respect to the covariates, we anticipate a small (<2%) amount of missing data. As the anticipated amount of missing data is small, we will analyse the data using a complete-case analysis.

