#### 4.6.2 Secondary outcomes

The secondary outcomes are:

- reasons given by supervisor and colleagues of former sew-ers (separately) for workers no longer being employed at Shahi
- proportions of sew-ers who state they are satisfied or very satisfied with work, feel valued or very valued at work, and are likely or very likely to stay with current employer
- change in self-assessed productivity
- self-report of having been approached by their assigned Captain and/or a supervisor
- change in attitude towards eye health, glasses wear and uptake of eyecare services
- changes in skill grade and associated change in wage
- adherence with spectacle wear
- Quality of Life using the THRIVE Near Vision Quality of Life tool.
- intervention cost-effectiveness

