#### 4.8 Sample size & power

Previous retention trials in this setting have showed 18-20% of overall likelihood of attrition at 5 months follow-up, 50% overall likelihood of attrition at 12 months, 60% at 18 months, 70% at 24 months. Assuming a work retention rate of 50% at 1 year and 40% at 18 months in the Control group, we anticipate that our glasses intervention will increase retention by 20% in the Intervention group at 1 year (hazard of 0.8). Data analysis using a Cox proportional hazard model with 2-sided significance at the 5% level and 80% power yields a total sample size of 1,260 (630 in each group). No correction for attrition is required as attrition is the outcome and therefore no attrition from the sample is possible.

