### 4.10.2 Data collection during trial

Wage and employment status data will be collected on a daily basis from Shahi's Human Resource division. Employment status data will be assessed on a weekly basis over the 18-month intervention period. Intervention costs will be collected by VisionSpring and assessed at the end of the trial intervention period. Secondary outcome data will be collected using the following data collection forms

- Baseline Assessment (following eye examination)
- Endline Assessment (at the end of the 18-month intervention period)
- Spectacle Wear Compliance (on a weekly basis over the 18-month intervention period)
- Self-assessment of productivity by workers enrolled in the trial (once at the start and at the end of the study)
- Supervisor assessment of worker productivity for workers enrolled in the trial (once at the start and at the end of the study)
- Identification of trial participants leaving the employ of Shahi will occur every two months and telephone interviews will be scheduled in two phases (7 months and 16 months after the start of assessment period)

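### SAP 8.3 expects minimal loss for secondary outcomes, but the retention assumed in 4.8 means about 56% of workers will have left by the month-18 endline; 8.3 and 9.1 also give two different missing-data rules for the primary analysis

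*SAP*

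**What the plan says.** Section 8.3 states that "we anticipate minimal loss-to-follow-up with respect to the primary outcome and for secondary outcomes". It then explains that leaving the company is itself the endpoint, but makes that argument for the primary outcome only. It adds a forecast of under 2% missing data, for covariates only. It concludes "We will perform complete-cases analyses in each case". The same paragraph warns that loss can bias the estimate, "particularly when there is differential drop out between intervention arms, which is related to the intervention".

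Section 4.8 sizes the trial on heavy attrition: "Assuming a work retention rate of 50% at 1 year and 40% at 18 months in the Control group". It expects glasses to "increase retention by 20% in the Intervention group at 1 year (hazard of 0.8"), and cites earlier experience of "18-20% of overall likelihood of attrition at 5 months follow-up".

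Section 4.10.2 places the "Endline Assessment (at the end of the 18-month intervention period"). The secondary outcomes in 4.6.2 include "proportions of sew-ers who state they are satisfied or very satisfied with work", with companion items on feeling valued and on likelihood of staying with the current employer, and also adherence with spectacle wear. Section 6 measures adherence by weekly observation of workers on the job, and 8.4 reports it as a weekly percentage for the whole trial. Section 7.1 promises intention-to-treat for every outcome.

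Section 9.1 prescribes 20 chained-equation imputations for missing data in the primary outcome analysis and says that the resulting datasets are averaged.

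**The concern.** The forecast of minimal loss is the stated reason for using complete cases. For anything that can be measured only while a worker is employed, it does not fit the attrition on which the trial was powered. Two consequences follow.

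- **Adherence.** A worker who has left cannot be observed at work. The weekly percentage is taken over fewer workers each week, and they are the ones who stayed. If non-wearers leave sooner, the percentage rises with no change in anyone's behaviour.
- **Work-attitude items at endline.** If only current employees are asked, the comparison conditions on the primary outcome. Suppose glasses retain some workers who would otherwise have left, and dissatisfied workers are likelier to leave. Intervention stayers could then look less satisfied with no true effect on satisfaction, and the result would carry an intention-to-treat label. This is the intervention-related drop-out that 8.3 itself describes as a source of bias.

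A separate, purely textual problem affects the primary analysis. Section 8.3 prescribes complete cases in every analysis and 9.1 prescribes imputation, so two analysts could both follow the SAP and produce different primary results.

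**Working it through.** **Inputs (SAP 4.8).** 630 per arm; control retention 50% at 12 months and 40% at 18 months; hazard ratio 0.8; two-sided 5% level; 80% power.

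**The plan's own figure.** Schoenfeld's formula gives 4 × (1.960 + 0.842)² / (ln 0.8)² = 631 events. Divided by 50% attrition this is 1,262, in agreement with the stated 1,260. The attrition figures are therefore what the design rests on.

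**Still employed at month 18.**
- Control: 630 × 0.40 = 252.
- Intervention, proportional hazards: 0.40^0.8 = 0.480; 630 × 0.480 = 303.
- Left: 1,260 − 252 − 303 = 705, or 56%.
- If the 20% increase means 50% rising to 60% at one year: ln 0.6 / ln 0.5 = 0.737; 0.40^0.737 = 0.509; 630 × 0.509 = 321; 687 left (55%).
- Robustness (assumption): if excluding planned leavers and counting rejoiners cut control attrition to 40%, the numbers are 630 × 0.60 = 378 and 630 × 0.60^0.8 = 419, with 463 left (37%).

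**Intervention workers observable for adherence (hazard ratio 0.8).**

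| Month | Control retention | Intervention retention | Observable of 630 |
|---|---|---|---|
| 5 | 80–82% | 83.7–85.3% | 527–538 |
| 12 | 50% | 57.4% | 362 |
| 18 | 40% | 48.0% | 303 |

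**Possible inflation of adherence at month 18 (assumptions).** Take wearers and non-wearers as two classes, with overall retention held at 48.0%. If 84.5% would wear glasses had everyone stayed (the closeout compliance that 4.2 reports for the earlier trial) and wearers leave at 0.9 to 0.7 times the hazard of non-wearers, the observed percentage is 1.0 to 3.5 points too high. The largest value, 6.3 points, needs 60% wear and a ratio of 0.7 together.

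**Possible bias in the proportion satisfied (assumptions).** No true effect; only current employees assessed; satisfaction standard normal with 50% satisfied at baseline; leaving hazard proportional to exp(−b × satisfaction); hazards calibrated to 40% and 48.0% retention.

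| b | Control stayers satisfied | Intervention stayers satisfied | Bias (points) | SE (points) | Coverage of 95% CI |
|---|---|---|---|---|---|
| 0.1 | 53.6% | 52.9% | −0.7 | 4.25 | 94.7% |
| 0.25 | 59.0% | 57.2% | −1.8 | 4.21 | 92.9% |
| 0.5 | 67.0% | 63.8% | −3.3 | 4.05 | 87.3% |

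Under the 50%-to-60% reading the bias is 1.0 / 2.3 / 4.3 points and coverage 94.4 / 91.3 / 81.1%. Under the 40% attrition case it is 0.4 / 1.0 / 1.9 points and 94.8 / 94.1 / 91.5%.

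**Missing-data rules side by side.** Section 8.3 has complete cases for each analysis, without exception. Section 9.1 has 20 imputed copies for the primary outcome, then averaging of the datasets. Averaging the datasets leaves one filled-in dataset and discards the between-imputation variance, so standard errors come out too small.

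**The case against.** Losing a job is not the same as being lost to follow-up. The SAP never restricts the endline to current employees. It sets self-assessed productivity for enrolled workers at the end of the study, and it shows that leavers can be reached by telephone. The attitude items refer to work and to the current employer without naming the company, so a worker employed elsewhere could answer. This stands. A reader might infer that the satisfaction items will certainly come from selected stayers, but the documents do not establish that. The SAP describes leaver interviews in two phases (months 7 and 16) and no endline for leavers, which makes the reading plausible; the protocol may settle it.

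The demonstrated harm is also modest. No document links satisfaction to leaving, and material distortion appears only at the strongest assumed link. A reader might infer that the secondary comparisons are seriously biased; the figures do not support that.

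For adherence, it can be said that wear at work is the definition, so a denominator of workers present is natural. That is fair, and the percentage is not invalid. The definition does not, however, make the loss minimal, and neither section 6 nor 8.4 says that the denominator will be reported.

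A reader might also think that a bounding analysis is essential. Trimming to workers who would stay under either arm removes (0.480 − 0.400) / 0.480 = 16.7% of Intervention stayers. That moves a 60% proportion to between 51.9% and 72.1%, far wider than the modelled bias. It also assumes that glasses never lead anyone to leave, and 9.3 describes departures for better-paid seasonal work, which leaves that uncertain. It cannot be called a requirement.

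Finally, the reference to averaging datasets may be loose wording for pooling estimates. If so, the correction is still needed, because the text as written describes a different procedure.

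**Conclusion.** The concern holds in a limited form. For outcomes that need current employment, minimal loss cannot be squared with 4.8: about 56% of workers will have left by month 18, and 37% even under a markedly more favourable assumption. For adherence this follows directly from the method of observation. For the satisfaction, feeling-valued and intention-to-stay items it depends on who receives the endline. If only current employees do, the comparison is not the one that 7.1 promises, with a likely bias of about 0.7 to 1.8 points against a standard error of about 4.2, larger only if leaving depends strongly on satisfaction. The employment-related loss does not affect the primary outcome.

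The conflict between 8.3 and 9.1 is a separate defect. It needs no inference, and it does bear on the primary analysis. Its numerical effect cannot be sized from the SAP and would be small if little is missing. Both matters should be corrected before analysis; neither undermines the design.

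**What to change.** 1. In 8.3, replace the minimal-loss premise for secondary outcomes with the attrition that 4.8 implies: 60% of controls and about 52% of Intervention workers gone by month 18 at a hazard ratio of 0.8.
2. State who receives the endline assessment. Report, per arm, the number still employed and the number analysed for each secondary outcome, and give the denominator for every weekly adherence percentage.
3. Label adherence, and any item collected only from current employees, as *conditional on continued employment*, with a matching exception in 7.1.
4. Optionally, add a bounds or retention-weighting sensitivity analysis with its assumptions stated. Bounds will be wide, and weighting targets a different quantity (all randomised workers, had they stayed).
5. Separately, choose one missing-data rule for the primary analysis and make 8.3 and 9.1 agree. If imputation is kept, fit the model in each of the 20 datasets and pool the estimates by Rubin's rules.

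The cost is SAP wording and a few extra table rows. No new data are needed, and the sample size does not change.

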## 4.6 Definition of primary and secondary outcomes

### 4.6.1 Primary outcome

The primary objective of the study is to estimate the effect of the provision of free reading glasses on the retention of textile workers employed in Shahi's sewing department. The time-to-event endpoint for PROSPER III is defined as the time between randomization to

Intervention or Control Group and loss of employment at Shahi. Employment status for each participant will be assessed from trial entry to closure as recorded in Shahi's Human Resource Management Database.

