## **9. COMPARATIVE ANALYSES**

### **9.1 Analysis of primary and secondary outcomes**

We will calculate the Cox proportional hazard ratio for the rate of retention between Treatment and Control groups with and without adjustment for the following co-variates: age, work tenure, spectacle wear compliance, self-reported self-efficacy, rural vs urban factory, hostel vs non hostel residence, marital and parental status, skill grade (if not too highly colinear with work tenure), work attendance. Linear regression analyses will be performed on potential determinants of primary and secondary outcomes. The study group and all significant variables with p values less than 0.20 in simple regression analyses will be included in multiple regression models. Histograms, normal quantile plots (QQ Plot), and the Shapiro-Wilk normality test will be used to test the normality assumption in regression models. For the Visual Quality of Life (THRIVE) tool, a composite score (eleven items) and near activities sub-score (five items) will be created on 0–100 scales. Intervention costs will comprise the screening test, glasses (and any replacement thereof) as well as direct and indirect costs to the company for facilitating workplace-based sight tests. We will report cost effectiveness distinguishing between study costs and program costs.

The analysis of primary and secondary outcomes will be adjusted for the minimisation factors (age, work tenure at the textile factory, efficiency during baseline assessment) to

account for the correlation between treatment groups introduced by balancing the randomisation. Both the crude unadjusted and adjusted estimates will be presented, but the primary inference will be based on the adjusted analysis.

For multiple imputation of missing data in assessing primary outcomes we will create 20 copies of the data, in which missing values shall be imputed by chained equations, and the datasets will be averaged.

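### SAP 8.3 (complete-case) and 9.1 (multiple imputation) give incompatible missing-data rules for the primary analysis; under 8.3, workers with a known outcome leave the adjusted model

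*SAP*

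**What the plan says.** **Outcome.** Section 4.6.1 takes employment status from trial entry to closure as "recorded in Shahi's Human Resource Management Database". Section 8.3 adds that leaving is itself the endpoint, so the outcome should be known for essentially every worker.

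**Missing data, first rule.** Section 8.3 states: "With respect to the covariates, we anticipate a small (<2%) amount of missing data". It then concludes: "As the anticipated amount of missing data is small, we will analyse the data using a complete-case analysis".

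**Missing data, second rule.** The last paragraph of section 9.1 provides for chained-equations imputation, with 20 copies, when the primary outcome is assessed. It does not refer to 8.3, and 8.3 does not refer to it.

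**Model.** Section 9.1 presents crude and adjusted estimates, but "the primary inference will be based on the adjusted analysis". The sentence before it has the analyses "adjusted for the minimisation factors (age, work tenure at the textile factory, efficiency during baseline assessment"). The opening paragraph of 9.1 gives a longer covariate list.

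**Population.** Section 7.1 defines intention-to-treat as "comparing the outcomes of all workers allocated to the Intervention Group with workers allocated to the Control Group". Section 9.6 expects that normally nothing is excluded from the full analysis set.

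**The concern.** A Cox model fitted to complete cases drops every worker with a blank in any covariate it contains. Here the outcome of those workers is known, so randomised workers and observed events are discarded for want of a baseline item. The primary estimate is then no longer the comparison that 7.1 defines. The crude hazard ratio keeps these workers and the adjusted one does not, so part of any difference between the two reflects who was analysed rather than the adjustment.

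If the imputation sentence in 9.1 governs, nobody is dropped. Because the SAP supports both, the choice could be made after the data are seen.

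**Working it through.** **1. Do the two rules conflict?** The imputation sentence in 9.1 could be read as covering missing outcomes only. But with HR-recorded employment, and leaving counted as the event, there is almost no missing outcome to impute. What can be missing in the primary analysis is mainly covariate data, and for those 8.3 says complete-case. Either 9.1 has almost nothing to act on, or the two sections give different rules for the same gaps.

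**2. Reproducing the planned size.** Inputs from 4.8: hazard ratio 0.8, two-sided 5%, 80% power, Control retention 50% at 12 months and 40% at 18 months, N = 1,260. Schoenfeld's formula with 1:1 allocation:

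- Events = 4 × (1.960 + 0.842)² / (ln 0.8)² = 4 × 7.849 / 0.0498, or 631.
- 631 / 0.50 = 1,262, against the stated 1,260.

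The size is therefore reproduced by applying a 50% event probability to both arms. This is inferred; the SAP does not state it.

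**3. Power with all workers kept.** Power = Φ(½ × √events × 0.2231 − 1.96).

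- 50% event rate: 1,260 × 0.50 = 630 events, power 80.0%.
- 18-month rates: 630 × 0.60 + 630 × (1 − 0.4^0.8) = 378 + 327 = 705 events, power 84.2%.

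**4. Power after complete-case deletion.** Events are assumed to fall in proportion to workers.

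| Reading of the 2% | Workers lost | Power, 18-month rates | Power, 50% rate |
|---|---|---|---|
| Overall, at its ceiling | 1,260 × 0.02 ≈ 25 | 83.5% (691 events) | 79.2% (617 events) |
| Each of five covariates, independently | 1 − 0.98⁵ = 9.6%, ≈ 121 | 80.4% | about 76% |

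The second row is an assumption. The SAP does not say whether its figure is per covariate or overall.

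**5. Which covariates can be missing?** Leaving out spectacle compliance and attendance, 9.1 names nine: age, tenure, self-efficacy, rural or urban factory, hostel residence, marital status, parental status, skill grade and baseline efficiency. Age and tenure define the randomisation strata (4.9), so both are needed to randomise. Rural or urban is a property of the factory. Baseline productivity is on the factory list given to the field team (4.9). Five remain, which is the basis of the second row. Even that is probably too high: demographic data come from the HR database (4.10.1), and a worker who misses a questionnaire tends to miss several items together.

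**6. Bias.** Missing baseline covariates should not depend on allocation. In 500 simulated trials with nine prognostic covariates, each 1.9% missing at random, neither the complete-case nor the filled analysis showed visible bias in the log hazard ratio. The loss was in precision.

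**The case against.** The strongest reply is that this hardly matters. The sentence placing the primary inference on the adjusted analysis closes the paragraph that names only age, tenure and baseline efficiency. Two of those are needed to randomise and the third is on a factory list. On that reading almost no one is deleted, and the 2% figure reads most naturally as an overall amount. This stands as to size. It does not remove the conflict between the sections, and because 9.1 also gives the longer list without saying which adjusted model is primary, the short list cannot be taken as settled.

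Four stronger readings are tempting, and the SAP does not support them:

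- **That complete-case is the settled rule.** The imputation sentence in 9.1 stands against it.
- **That power at 18-month event rates drops clearly below 80%.** Reaching 77.2% takes 2% independent missingness in all nine covariates (1 − 0.98⁹ = 16.6% lost), including age, tenure and factory location.
- **That 4.8 is wrong in saying "therefore no attrition from the sample is possible".** That sentence concerns attrition as the outcome, not blank covariates. It is fair to say only that the size carries no allowance for analytic exclusions.
- **That the treatment effect is biased.** Nothing in the plan suggests that missing baseline items would differ by arm.

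**Conclusion.** The point holds as a contradiction between 8.3 and 9.1 that leaves the primary missing-data rule open. Under 8.3, it also departs modestly from the intention-to-treat comparison in 7.1. At the plan's own figure taken overall, the effect is at most about 25 of 1,260 workers and under one point of power on either event-rate basis. A loss of several points needs two assumptions together: 2% for each covariate, and the longer list as the primary model. The crude and adjusted hazard ratios would remain broadly comparable at the smaller loss, though not computed on the same workers.

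The figures rest on Schoenfeld's formula, a hazard ratio of 0.8, and missingness unrelated to arm and outcome. The point is worth correcting because the remedy is cheap and removes a choice that could otherwise be made late, not because the trial's conclusion is at risk.

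**What to change.** In 8.3, replace complete-case analysis for covariates with a single rule: every randomised worker stays in the primary adjusted Cox model, and missing baseline covariates are filled without regard to arm. Either of two methods would serve, and one must be named:

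- the mean (or most frequent category) over both arms combined, plus a missing-value indicator; or
- the chained-equations imputation already in 9.1. In that case 9.1 should also say that the 20 estimates are combined by Rubin's rules, since it now speaks of averaging the datasets.

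Amend the imputation sentence in 9.1 to match, so that only one rule remains, and keep the complete-case fit as a sensitivity analysis. Make both edits before unblinding.

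The rule covers baseline covariates only and assumes that they are recorded independently of allocation. Spectacle compliance, and attendance if measured during follow-up, can depend on arm or outcome and are a separate issue.

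Cost: SAP wording and a few lines of code, with no new data. With the mean-fill method the coefficients of the filled covariates become slightly less interpretable, but they are not the target of inference.
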